2. STUDY DESIGN

Study design: Single-blind study. Patients will be randomized, at the time of implant, to HBP versus CS pacing, and remain blinded to their treatment allocation. Both treatment options use standard-of-care, FDA-approved devices. The distinction is only in the allocation toward HBP and CS pacing. Treating physicians will be aware of assignment in order to facilitate routine device follow-up. Echocardiographic and electrocardiographic evaluation will also be performed in a blinded manner.

Cross-over is permitted between treatment group allocation if:

- CS lead cannot be placed due to difficult cannulation of the CS, limited branches at the posterolateral or lateral wall, or phrenic nerve capture. These patients may then cross-over to HBP.
- HBP patients may cross-over if lead cannot be positioned with adequate stability and reasonable pacing output or if QRS width does not narrow by at least 20% or to a QRS width of \leq 130 msec.

Implant procedure will be per routine percutaneous access, as is standard for pacemaker and ICDs. All patients will receive an FDA-approved cardiac resynchronization therapy pacemaker or defibrillator device, as per standard of care outlined for the patient. In order to facilitate optimal lead placement, arterial access for levo-phase CS angiography and/or LV septal mapping to characterize site of bundle-branch block may also be performed, at the discretion of the implanting physician per his/her standard practice.

Follow-up will be performed at 2 weeks post-implant for incision check and device interrogation as is standard of care. In addition, routine device and clinical follow-up will be scheduled at 1, 3, 6, and 12 months.

Electrocardiography (i.e., ECG) will be performed pre-implant, prior to hospital discharge, at 3 months, 6 months, and 12 months. Echocardiography will be performed pre-implant, 6 months, and 12 months to evaluate for change in LVEF, chamber dimension, and wall motion with strain imaging as is standard of care in the treatment of patients with advanced heart failure. NYHA functional class and quality of life (utilizing the Kansas City Cardiomyopathy Questionnaire) will be assessed pre-implant and at 6 months.

Duration of study: 12 months

Primary endpoints: A combination of clinical, electrocardiographic, and echocardiographic endpoints will be prospectively studied. These include:

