- **Clinical:** Primary clinical endpoint is a composite of heart failure hospitalization, VT/VF, and any-cause mortality at 12 months.
- **Electrocardiographic:** Change in QRS duration between pre-implant and at hospital discharge, 3 months, 6 months, and 12 months will be performed by readers blinded to treatment allocation. Arrhythmia occurrence (i.e., AF, nonsustained VT, VT or VF requiring device therapy) will be documented throughout the study period
- **Echocardiographic:** Change in left ventricular ejection fraction, chamber dimension, and tissue-strain pre-implant, at 6 months, and at 12 months to be performed by readers blinded to treatment allocation

Primary safety endpoint: Procedure-related complications will be assessed prospectively both acutely and throughout the study period, including:

- **Procedure related:** pneumothorax, perforation, pericardial effusion, or hemorrhage
- **System related:** implant site hematoma, implant site infection
- **Lead related:** lead dislodgement, lead fracture, inability to pace due to high threshold, phrenic capture

Randomization scheme: Patients will be allocated to HBP or standard CS lead at time of implant. Patients with LBBB and non-LBBB will be assigned to separate blocks and randomized separately.

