6. STATISTICAL PLAN AND CONSIDERATIONS

Sample size estimation:

The sample size for this study is a total of 40 subjects (20 HBP and 20 CS lead). The sample size estimate was based on a goal to observe an absolute 10% difference in LVEF between the two groups, leading to a Cohen's d statistic of 1. With a significance level (α) = 0.05 and a power of 0.8, at least 17 subjects will be required in each group. A goal of 40 subjects was made to allow for possible dropout during the study period.

Statistical methods:

Patients will be studied based on the final treatment allocation. Crossovers and reasons for crossover will also be recorded. Fisher's exact or the Chi-Square test will be used for categorical variables, and continuous parameters will be compared by the two-tailed unpaired Student's t test and the F test for analysis of variance (ANOVA), as needed. Kaplan-Meier method will be used for computing the event free survival curves. Each implant strategy will be compared within this cohort of patients for its impact on percent change QRS duration, LVEF, and as clinical outcome. Multiple logistic regression and multiple regressions using the Cox proportional hazards model will be performed to determine the independent association of each of the implant variables with LVEF and clinical outcome.

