10. STUDY MONITORING, AUDITING AND INSPECTING

All periprocedural complications and adverse events will be reviewed by PIs at study midpoint to ensure there is no significant difference in event rate between the study groups. Should there be significant differences, or if there should be a high overall event-rate out-of-line with the procedural norm for CRT, the study will be halted.

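### The final-allocation rule has no exception for the primary safety endpoint, so a listed complication of a failed first lead attempt is counted against the replacement lead, which may shrink or reverse the HBP v CS safety comparison

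*Combined protocol and SAP*

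**What the plan says.** **Safety endpoint (section 2, primary safety endpoint).** Complications are assessed prospectively at implant and during follow-up, under three headings. The procedure-related list includes perforation and pneumothorax. The system-related list has implant-site haematoma and infection. The lead-related list is "lead dislodgement, lead fracture, inability to pace due to high threshold, phrenic capture".

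**Crossover (section 2, study design).** A patient allocated to CS may switch to HBP if the "CS lead cannot be placed due to difficult cannulation of the CS, limited branches at the posterolateral or lateral wall, or phrenic nerve capture". In the other direction, "HBP patients may cross-over if lead cannot be positioned with adequate stability and reasonable pacing output", or if the QRS does not narrow enough. Aim 1 (section 1B) and the implant procedures (section 5) also send a failed first site to the other one.

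**Grouping (section 6, statistical methods).** "Patients will be studied based on the final treatment allocation". The next sentence says that crossovers and their reasons are recorded. No separate grouping is given for safety.

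**Logging and review (sections 8 and 10).** Complications are logged by procedure, system and lead. The plan does not say whether the attempted lead or the final lead carries the event. The investigators review events at the midpoint "to ensure there is no significant difference in event rate between the study groups", and significant differences halt the study. The groups are not defined there.

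**The concern.** A patient whose first attempt fails has been exposed to two implant attempts. Grouping by final lead places the whole patient, including any harm from the first attempt, under the second lead. A perforation during a CS attempt that ends with a His lead becomes an HBP complication. If a high threshold found at the His site is logged as a complication and the patient then receives a CS lead, it becomes a CS complication.

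Hypothesis (a) in section 1B is that HBP can be achieved safely, and periprocedural complications are an acute outcome under Aim 2. Under the section 6 rule, a lead type whose failures come with a listed event loses those events to its comparator. If the midpoint review uses the section 6 groups, the halting decision would rest on the same counts.

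**Working it through.** **Inputs from the documents.** Section 6: 40 patients, 20 per arm, and one grouping rule. Section 2: the safety list and the switch criteria. Crossover and complication rates are not stated, so every event count below is an assumption.

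**The plan's own figure.** Section 6 sizes the trial on LVEF only: "With a significance level (α) = 0.05 and a power of 0.8", Cohen's d = 1, 17 per group. A two-sided unpaired t test gives n = 16.71, hence 17, with power 0.807. The figure reproduces. There is no corresponding calculation for safety, so the check is a count.

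**Overlap between switch triggers and the safety list.**
- Phrenic capture appears in both, almost word for word.
- Failure to reach a reasonable pacing output is close to failure to pace because of a high threshold.
- Poor stability while positioning is related to dislodgement but is not the same thing.
- Difficult cannulation, limited venous branches and insufficient QRS narrowing are not on the list.
- Perforation is on the list but is not a trigger. It still follows the patient if it occurs during an attempt that is then abandoned.

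**Formulas.** Let a and b be the numbers switching HBP to CS and CS to HBP. Let x ≤ a and y ≤ b be those with a countable event from the first attempt. Let u and v be patients with events among those who keep their HBP or CS lead.
- By randomised arm: HBP (x + u)/20, CS (y + v)/20.
- By final lead: HBP (u + y)/(20 − a + b), CS (v + x)/(20 − b + a).

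| Assumed a, b; x, y; u, v | Randomised arm, HBP v CS | Final lead, HBP v CS |
|---|---|---|
| A: 6, 2; 6, 2; 0, 0 | 6/20 (30%) v 2/20 (10%) | 2/16 (12.5%) v 6/24 (25%) |
| B: 6, 2; 2, 1; 2, 1 | 4/20 (20%) v 2/20 (10%) | 3/16 (18.8%) v 3/24 (12.5%) |
| C: 1, 0; 1, 0; 1, 1 | 2/20 (10%) v 1/20 (5%) | 1/19 (5.3%) v 2/21 (9.5%) |
| D: 6, 0; 0, 0; 2, 2 | 2/20 (10%) v 2/20 (10%) | 2/14 (14.3%) v 2/26 (7.7%) |

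HBP minus CS moves from +20 to −12.5 points in A (reversal), from +10 to +6.3 in B (smaller, same sign), from +5 to −4.3 in C (one patient is enough), and from 0 to +6.6 in D. In D no trigger is counted and only the denominators change, to the disadvantage of HBP. The bias has no fixed direction.

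**By lead attempted.** If a patient with two attempts enters both denominators, the HBP denominator in A and B is 20 + 2 = 22 and the CS denominator is 20 + 6 = 26. A gives 6/22 (27.3%) v 2/26 (7.7%). B gives (2 + 2)/22 = 4/22 (18.2%) v (1 + 1)/26 = 2/26 (7.7%). Both keep the direction seen by randomised arm.

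**Midpoint, only if its groups are the final-lead groups.** Assume 10 per arm, five HBP switchers each with a countable event, and no other events. By arm this is 5/10 v 0/10 (Fisher p = 0.033). By final lead it is 0/5 v 5/15 (p = 0.27).

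**The case against.** **The triggers may not be counted at all.** The switch criteria describe a lead that could not be placed or positioned. No section says that such a finding, resolved by going to the other site, is logged as a complication. This stands. Including acute events makes that reading natural but does not establish it. A listed event that is plainly a complication, such as perforation during the abandoned attempt, still moves.

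**Reversal is built into scenario A.** This also stands. If every switcher has a countable event and nobody else has any, unequal numbers of switchers reverse the direction by algebra. Scenario B, with the same switch counts, does not reverse. A reader might infer that the plan will make the less safe lead look safer, but the documents do not support that. The overlap is partial, the rates are unstated, and D moves the comparison against HBP.

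**The differences are within chance.** For A, Fisher p is 0.24 by arm and 0.44 by final lead, and the trial is not sized for safety. That limits what any safety table can show. It does not justify a grouping that misassigns events.

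**Failures remain visible.** Crossover reasons are recorded and Aim 1 reports the success rate of His lead placement. Events could be traced back, but the stated comparison does not use that information.

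**The halting effect is conditional.** A reader might infer that the midpoint review is certain to use misassigned counts. Section 10 does not define its groups, so this is a possibility only. The second halting criterion there, a high overall event rate, does not depend on grouping.

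**Later revision.** A reader might extend the point to leads revised during follow-up. The documents describe crossover when the allocated lead cannot be placed at implant and do not say that a later revision changes the final allocation.

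**Conclusion.** The point holds as a fault in the stated grouping. Section 6, as written, assigns a listed complication of a failed first attempt to the lead that replaced it, and nothing elsewhere exempts the safety endpoint. The HBP v CS safety comparison is biased whenever such events occur, and it may shrink or reverse.

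The size cannot be fixed from the documents. Under assumed counts the shift ranges from a modest reduction (+10 to +6.3 points) to a reversal (+20 to −12.5 points). The larger shifts require that triggers found at implant are logged as complications. All of the figures read the final allocation as the lead finally implanted, which is the plain sense given the crossover sentence that follows it.

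**What to change.** 1. **Section 6:** exempt the safety endpoint from the final-allocation rule and compare complication rates by randomised arm.
2. **Section 6, supporting table:** tabulate lead-related and implant-attempt events by the lead being attempted or in place when the event occurred, with a patient who had two attempts in both denominators. Report events tied to neither lead, such as pneumothorax, haematoma and infection, by randomised arm only.
3. **Section 2:** state whether a switch trigger resolved during the implant counts as a safety event.
4. **Section 10:** define the study groups in the midpoint review as the randomised arms.

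The switch criteria themselves need no change for this. The cost is protocol wording and one extra field on the complication log for the lead attempted or in place. The HBP complication rate may look less favourable than under the present rule.

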3. SUBJECT SELECTION AND WITHDRAWAL

Sites:

Subjects selected for study will be recruited from eight sites: The University of Chicago Medical Center (Chicago, IL), the Ronald Reagan UCLA Medical Center (Los Angeles, CA), Northwestern University's Northwestern Memorial Hospital (Chicago, IL), Geisinger Cardiology of the Geisinger Health System (Wilkes-Barre, PA), Indiana University Krannert Institute of Cardiology (Indianapolis, IN), Rush University Medical Center (Chicago, IL), Edward Elmhurst Healthcare Edward Hospital (Naperville, IL), Baptist Health Louisville (Louisville, KY). Each site will function independently but follow the same treatment protocol. Each site will maintain

their own randomization schedule. The data from the UCLA, NWU, Geisinger, IU, Rush, Edward, and Baptist Health sites will be shared with the University of Chicago at study completion for data analysis only.

Baptist Health Louisville has formally requested the University of Chicago IRB to serve as its own IRB. The following individuals from Baptist Health will be engaged the conduct of this study in Louisville with the following roles:

- [name] – Principle Investigator
- [name], APRN – Sub-Investigator
- [name] – Research Coordinator
- [name] – Research Coordinator

All of the study team members at Baptist Health have provided their curricula vitae, as well as confirmation of appropriate human subjects protection training.

Eligibility:

Eligible patients will be similar to those previously enrolled in the large randomized controlled trials which guide current indications for CRT. This includes:

- Patients at least 18 years of age
- LV systolic dysfunction with LVEF $\leq 35\%$
- Evidence of intraventricular conduction delay with QRS duration > 120 msec
- NYHA Class II, III, and ambulatory Class IV heart failure with either ischemic or nonischemic cardiomyopathy and patients with NYHA Class I symptoms and ischemic cardiomyopathy

Inclusion:

Inclusion criteria are identical to those presently accepted by the American Heart Association (AHA)-American College of Cardiology (ACC)-Heart Rhythm Society (HRS) for CRT.²⁸ These include:

- 1) Left ventricular ejection fraction (LVEF) $\leq 35\%$, sinus rhythm (SR), left bundle-branch block (LBBB) morphology, and QRS duration ≥ 150 msec, and NYHA Class II, III, or ambulatory Class IV patients on goal-directed medical therapy (GDMT) [Class I]
- 2) LVEF $\leq 35\%$, SR with LBBB with QRS 120-149 msec on GDMT [Class IIa]
- 3) LVEF $\leq 35\%$, SR with non-LBBB with QRS ≥ 150 msec on GDMT [Class IIa]
- 4) LVEF $\leq 35\%$, in AF if medication or AV nodal ablation will allow near 100% pacing [Class IIa]
- 5) LVEF $\leq 35\%$ undergoing new or replacement device with anticipated $>40\%$ ventricular pacing on GDMT [Class IIa]
- 6) LVEF $\leq 30\%$, ischemic etiology of HF, SR with LBBB ≥ 150 msec and NYHA Class I symptoms on GDMT [Class IIb]
- 7) LVEF $\leq 35\%$, SR with non-LBBB with QRS 120-149 msec, NYHA Class III/ambulatory Class IV HF on GDMT [Class IIb]

LVEF $\leq 35\%$, SR with non-LBBB with QRS ≥ 150 msec, NYHA Class II HF on GDMT [Class IIb]

Exclusion:

Exclusion criteria include:

- Existing CRT device
- Inability of patient capacity to provide consent for themselves either due to medical or psychiatric comorbidity
- Pregnancy
- Participation in other trials
- Difficulty with follow-up

No payments will be made to subjects to participate.

4. STUDY DEVICE

His-bundle lead pacing will be performed with the Medtronic SelectSecure™, Model 3830 lead. Delivery of the lead utilizes a deflectable sheath, the Medtronic SelectSite™, Model C304. Both devices are FDA approved for the purpose of his-bundle pacing. It is the only device available which is presently FDA approved for selective His pacing.

The lead has not been subject to any FDA advisories or recalls. Current lead performance is regularly reported and available at:

<http://www.medtronic.com/productperformance/model/3830-selectsecure.html>

CS lead and CRT device generator selected for implant will be left to the discretion of the operator. Only FDA approved CS leads and CRT generators will be utilized in the study. There are five present manufacturers of CS leads and CRT generators: Biotronik, Boston Scientific, Medtronic, Sorin, and St. Jude Medical. The University of Chicago utilizes all five vendors, and there is no convincing data to suggest the superiority of any one vendor over the others.

5. STUDY PROCEDURES

Pre-Implant

- Patients will be screened for study
- Pre-implant ECG reviewed (to be performed on day of screening)
- Baseline transthoracic echocardiogram (TTE) reviewed (does *not* need to be performed during inpatient hospitalization; outpatient or outside-hospital TTE report may also be performed)
- Patients who screen-in will be provided Kansas City Cardiomyopathy Questionnaire
- NYHA functional class to be determined by treating physician
- Operating physician will be informed of patient allocation to facilitate planning of procedure

Randomization, Implant, and Periprocedure Care

- RA and RV leads will be positioned per routine
 - o Arterial access for CS angiography or LV septal mapping may be performed at the discretion of the implanting physician in order to facilitate optimal lead placement

- 'LV' lead will be positioned in CS or at His-bundle based on allocation assignment
 - o The allocation assignment will be based on randomization schedule (developed using random number generator)
 - o The study coordinator will keep allocations in a sealed envelope and provide to implanting physician at time of procedure
 - o Patients with LBBB and non-LBBB will be randomized separately
 - o Each independent site will maintain their own randomization schedule
- If the initial allocated site is unsuccessful, alternative site will be pursued
- Intracardiac EGM information (surface QRS to LV site or QLV), pacing output, and lead position at final site will be recorded
- Predischarge ECG performed
- Predischarge device interrogation will be performed (as per standard of care)

2-Week Incision Check

- As per routine post-device care, all patients will be scheduled for routine postoperative device check at 2 weeks to evaluate incision
- Device interrogation (as per standard of care)

1-Month Visit

- Routine device interrogation
- Routine clinical check

(Note: Week 2 and Month 1 visits may be combined, per treating doctor discretion, for the simple post-op wound and clinical visit)

3-Month Visit

- Routine ECG
- Routine device interrogation
- Routine clinical check

6-Month Visit

- Post-implant TTE
- Routine ECG
- Routine device interrogation
- Routine clinical check
- Administration of Kansas City Cardiomyopathy Questionnaire
- NYHA functional class to be determined by treating physician

12-Month Visit

- Post-implant TTE
- Routine ECG
- Routine device interrogation
- Routine clinical check
- Administration of Kansas City Cardiomyopathy Questionnaire
- NYHA functional class to be determined by treating physician

Contact between study visits

- Patients will be enrolled in remote device monitoring (as all CRT patients are) and device alerts will be monitored per routine
- Any hospitalizations will be flagged for review

Future contact

- Patients will be asked to participate in an extended registry to evaluate longer-term clinical outcome after study completion. We will collect data from subjects' medical record for 2 years following their participation in the study. Data collected will include cardiac imaging results, and other clinical events such as hospitalization and death.

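### Sixteen short site-held lists for 40 patients, with no block size stated, do not reliably deliver the 20:20 split or LBBB balance, and the t test does not adjust for LBBB

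*Combined protocol and SAP*

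**What the plan says.** Section 3 (Sites) states: "Subjects selected for study will be recruited from eight sites". The sites work independently under a common protocol and send their data to the University of Chicago at study completion, for analysis. Sections 3 and 5 both leave the schedule with the site; section 5 reads "Each independent site will maintain their own randomization schedule".

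Section 2 (Randomization scheme) adds: "Patients with LBBB and non-LBBB will be assigned to separate blocks and randomized separately". In context, the word blocks there names the two strata. Section 5 describes how the sequence is made: "The allocation assignment will be based on randomization schedule (developed using random number generator"). The study coordinator keeps the assignments in sealed envelopes. No section gives a block size, a permuted-block rule, a central list or a cap on either arm.

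Section 6 nevertheless plans on equal arms: "The sample size for this study is a total of 40 subjects (20 HBP and 20 CS lead"). It supports this with: "With a significance level (α) = 0.05 and a power of 0.8, at least 17 subjects will be required in each group". Continuous outcomes are compared by a "two-tailed unpaired Student's t test". The logistic and Cox models in the same section are for implant variables, and the LBBB stratum is not named as a term in any model.

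**The concern.** Stratified randomisation balances a factor only if the sequence within each stratum is blocked and most blocks fill. Lists averaging 2.5 patients often stop partway through a block. The leftover imbalances from up to 16 lists then add together, both in the arm totals and within the LBBB stratum.

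The investigators chose LBBB as the one patient characteristic to balance. If it is unbalanced by chance, an unadjusted comparison of QRS or LVEF change carries part of the LBBB versus non-LBBB difference along with the treatment difference. In a trial of 40, whose stated hypothesis is that the two strategies give similar results, that is avoidable noise. A shortfall in one arm would also use up the margin between 17 and 20 that section 6 keeps for dropout.

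**Working it through.** **Inputs from the document.** Eight sites (section 3); two strata (section 2); 40 patients, 20 per arm (section 6); "absolute 10% difference in LVEF between the two groups, leading to a Cohen's d statistic of 1" (section 6), hence an implied SD of 10 points; two-sided alpha 0.05 and power 0.80.

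**Assumed, because the document gives no figure.** LBBB share 50% or 70%; site recruitment equal, or skewed with random unequal site shares; lists unblocked, or permuted blocks of 2, 4 or 6.

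**1. The plan's own figure.** Exact t-test power uses noncentrality d × √(n₁n₂/(n₁+n₂)) on n₁+n₂−2 degrees of freedom. With d = 1:

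- 16:16: √(256/32) = 2.828, power 0.781
- 17:17: √(289/34) = 2.915, power 0.807

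So 17 per arm is correct for equal arms.

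**2. List count.** 8 × 2 = 16 lists; 40/16 = 2.5 patients per list.

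**3. A hand check for blocks of 2.** A list contributes ±1 to the arm difference if it ends on an odd count, and 0 otherwise. With so few patients per list, about half the lists (8 of 16) end odd. With exactly 8 odd lists:

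- P(exact 20:20) = C(8,4)/2⁸ = 70/256 = 27%
- P(24:16) = 2/256 = 0.8%, since all eight must fall the same way

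**4. Simulation of 40 patients over the lists.**

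| Scheme | Exact 20:20 | Smaller arm under 17 | LBBB share differs by about 10 points or more |
|---|---|---|---|
| 16 local lists, blocks of 2 | 27–30% | about 1% | 15–17% |
| 16 local lists, blocks of 4 | 21–23% | 4–6% | 26–31% |
| 16 local lists, blocks of 6 | 18–21% | 8–12% | 33–40% |
| 16 local lists, unblocked | 12.5% | 27% | 50–55% |
| Central, 2 lists, unblocked | 12.5% | 27% | 50–55% |
| Central, 2 lists, blocks of 2 | about 75% | 0% | 0% |
| Central, 2 lists, blocks of 4 | about 63% | 0% | under 1% |
| Central, 2 lists, blocks of 6 | about 50% | 0% | at most about 1.5% |

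The unblocked arm totals are simply Binomial(40, 0.5): C(40,20)/2⁴⁰ = 0.125, and 2 × P(X ≤ 16) = 0.268.

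**5. Sensitivity.** I re-ran this with 10,000 trials per scenario. The last column depends on how differences of exactly 10 points (for example 12/20 against 10/20) are counted. Counting all of them gives about 18–22%, 28–34% and 36–43% for local blocks of 2, 4 and 6, and at most 2.5% for central blocks. Fixing exactly five patients at every site puts the smaller arm under 17 in about 1%, 5–7% and 13–15%. The contrast between local and central blocked lists is unchanged.

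**6. Power after imbalance (d = 1).**

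| Split | Power |
|---|---|
| 20:20 | 0.869 |
| 24:16 | 0.855 |
| 26:14 | 0.836 |
| 28:12 | 0.806 |
| 17:17 (34 analysed) | 0.807 |
| 20:14 (34 analysed) | 0.795 |
| 22:12 (34 analysed) | 0.771 |

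**7. What LBBB imbalance does to an unadjusted mean.** The shift equals the share difference times the LBBB versus non-LBBB difference in mean outcome. The document does not give the latter. If it were 5 or 10 LVEF points, a 10-point imbalance would shift the comparison by 0.10 × 5 = 0.5 or 0.10 × 10 = 1.0 points. A 20-point imbalance would shift it by 1.0 or 2.0 points, against a design difference of 10.

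**The case against.** **The large unblocked figures are not about site-held lists.** This is correct. One unblocked central list per stratum gives the same 27% and 50–55% as sixteen unblocked local ones. Only the blocked rows of the table measure the effect of holding lists locally. Central holding without blocking would repair nothing.

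**Local stratification still does something if the lists are blocked.** Also correct. With blocks of 4, the LBBB share differs by 20 points or more in about 2–5% of trials, against 17–22% unblocked. A reader might infer that the stratification is worthless; the figures do not support that. They show it working much less well than it could.

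**Falling under 17 is not a cliff.** A reader might infer that the trial loses its power. It does not: 17 is the minimum for equal arms, and before dropout power stays above 0.80 down to 28:12. A split worse than that has probability of about 0.6% even unblocked. With 34 analysed, a 20:14 split costs about one point (0.807 to 0.795).

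**Predictable allocation.** A reader might infer selection bias from short local blocks and unblinded physicians. Section 5 specifies sealed envelopes held by the coordinator, no block size is stated, and lists that stop early contain few forced assignments. The document gives no basis for sizing such a bias, so the point does not rest on it.

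**Crossover.** Analysis by final treatment can move the split under any randomisation scheme. That is a separate matter.

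**Site-held lists have a purpose.** They suit sites that run independently, and they give some balance on operator and site, which an LBBB-only central list gives up. This stands as a real trade-off. Exact 20:20 is not guaranteed centrally either (about 63% with blocks of 4), but there the smaller arm does not fall under 17.

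**Conclusion.** The point holds in a limited form. As written, the procedure does not reliably deliver the 20:20 split or LBBB balance that the plan intends, and the section 6 comparison does nothing to compensate. If the lists are blocked locally, a 10-point LBBB imbalance arises in roughly 15–40% of trials depending on block size, against at most about 1.5% (2.5% counting every exact 10-point difference) with one blocked central list per stratum. If they are unblocked, the figure is about 50–55%, and the cause is the lack of blocking.

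The consequence is chance imbalance entering unadjusted QRS and LVEF comparisons, plus some erosion of the dropout margin. It is not a systematic bias, and it is not a material loss of power. The result rests on assumed LBBB shares, site shares and block sizes. The direction holds over all the values tried; the size varies. It is worth correcting because correction is easy, but it does not invalidate the design.

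**What to change.** 1. **Section 6.** Include the LBBB stratum in the QRS and LVEF comparisons, for example a linear model with treatment and LBBB in place of the unpaired t test. This costs wording and one degree of freedom, and it helps whichever randomisation scheme is used.

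2. **Sections 2, 3 and 5.** Replace the site schedules with one schedule held at the University of Chicago, already the analysis centre. Stratify it by LBBB, use permuted blocks of varying size, and release assignments one patient at a time. Blocking must be stated, since central holding alone does not help. If balance by site is also wanted, use central minimisation on LBBB and site with a random element. The cost is protocol wording and a contact at the coordinating site during implant hours, and less site balance if LBBB is the only stratum. No visit, treatment or sample size changes.

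3. **If site lists are kept.** State the block rule in section 5, and describe 20:20 in section 6 as a target. Change 1 then matters more.
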